4.1.2.2 Study populations (part II – event based)

For part II (ODP/ODT), the following specifications as to analysis sets apply:

With respect to the evaluation of efficacy, surrogate efficacy and safety of the single or repetitive intravenous infusions of BT524, each bleeding event will be considered as an individual case in the primary analysis.

There are 2 event-based analysis sets:

Full Bleeding Event Set (FBE)

All events treated with any portion BT524, and with at least one efficacy assessment.

Per Protocol Bleeding Event Set (PPBE)

Subset of FBE of patients who are compliant with the study protocol (i.e. without any major protocol deviations in part II) and includes all bleeding events without any major protocol deviation with potential to impact the results of the efficacy analysis.

In the BDRM, dated 25-Jun-2020, all minor and major protocol deviations on bleeding event level were reviewed and agreed upon. Following from the decisions taken, assignments to PPBE analysis population were done. A complete list of all protocol deviations is attached to the BDRM minutes and included in the listings of the final analysis.

As agreed in the BDRM (25-Jun-2020), all bleeding events documented for a patient with at least one major protocol deviation (i.e. patients excluded from PP II set) will be excluded from the PPBE.

In addition, selected efficacy analyses for bleeding events and surgical interventions will be analyzed per patient in the FBE and PPBE populations as defined above.

With respect to the evaluation of adverse events, the patient is the relevant unit for analyzing these endpoints. Therefore, their evaluation across all parts is based on the safety population as defined in section 4.1 above.

5 General Statistical Methods and Definitions

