## 13.2 Duration of the Study

First Patient in	Adults: 20-Mar-2013 Children/Adolescents (≥ 6 to < 18 years): 09- Nov-2014 Children < 6 years: Q2/2018 (planned)
Last Patient Last Visit (planned)	Q1/2020

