#### Part II ODP/ODT

With respect to the evaluation of efficacy, surrogate efficacy and safety of the single or repetitive intravenous infusions of BT524, each bleeding event will be considered as an *individual case* in the primary analysis; in addition efficacy analysis for bleeding events and surgical interventions will be analyzed as repeated measurements per subject in the ITT and PP populations.

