### 15.2.6 Safety Analysis

Adverse events (AEs) will be coded by means of the MedDRA® dictionary. Incidence rates (i.e. number and percentage of affected patients) will be calculated for the coding levels *system organ class* and *preferred term*. Further analyses of AEs will focus on seriousness, intensity, causal relationship to study medication, and outcome. Serious adverse events (SAEs) will be displayed in detail.

Safety laboratory assessments will be categorized with respect to the laboratory specific reference ranges as normal/abnormal. Abnormal values will be further classified with respect to clinical relevance. Changes over time will be described by means of "shift-tables".

Safety analysis will be based on the safety population.

Descriptive methods will be applied for all variables of safety. Details will be provided in the statistical analysis plan.

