11.1 Adverse events

All assessments will be done for all patients, part I and part II separately.

Adverse events (AE) will be coded using the MedDRA® dictionary. The current version will be used at time of database lock and presented by primary System Organ Class (SOC) and Preferred Term.

The analysis will focus on the treatment-emergent AEs (TEAEs). When an AE occurs after written consent has been obtained but before the first dose of study drug, the AE will be considered a non-treatment emergent AE. An AE that occurs (or worsened) on or after the time the patient receives his/her first dose of study drug (until his/her last study visit) will be considered a treatment emergent AE (TEAE). See also CSP section 14.6.2 for definition of non-treatment adverse events.

Please note the definition of study periods and adverse event reporting periods in section 5.5 above. Please also note that analyses for TEAE will be based on the safety population (SAF). Overview tables including non-TEAEs will be based on the APE to also include patients not treated in the study.

For the analysis of TEAEs only those TEAEs are taken into consideration which are reported from first treatment to the safety visit after treatment (independent of the planned duration between treatment start and Day 49 safety visit). For part I this is the duration between PK treatment and the Day 49 PK safety visit or earlier (if a bleeding event happened before Day 49 PK safety visit), and for part II this is for each bleeding event the duration between treatment of the bleeding event and Day 49 safety visit or earlier (if another bleeding event happened before Day 49 safety visit).

All other TEAEs reported out of these time frames will be counted and listed. Exception is the analysis of related serious adverse events (related SAEs) which are included in the analysis irrespective of the onset time after first administration of IMP:

If 'Day 49 safety visit' is not done, the period for inclusion of TEAEs in the analysis is from baseline (treatment start) to 49 days post-baseline.

The total number and percentage of patients reporting at least one AE and the absolute count of AEs will be tabulated for each age group and overall. This initial summary will be based on the APE set and provide a breakdown of the following:

- Any AE
- Any non-severe AE
- Any TEAE
- Any non-serious TEAE
- Any non-severe TEAE
- Any treatment-related TEAE
- Any severe AE

- Any severe TEAE

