- Any severe treatment-related TEAE
- Any SAE
- Any serious TEAE
- Any serious treatment-related TEAE
- Any AE leading to discontinuation from study
- Any TEAE leading to discontinuation from study
- Any treatment-related TEAE leading to discontinuation from study
- Any AE with outcome of death
- Any death
- Any pregnancy

In the SAF number and frequencies (i.e. percentages) of patients with TEAEs will be given by System Organ Class (SOC) and by Preferred term within each SOC (total, for each age group) together with the number of events for the following:

1. All TEAEs
2. Serious TEAEs
3. All TEAEs considered related (see details below)
4. Serious TEAEs considered related (see details below)
5. All TEAEs by maximum severity ('mild', 'moderate', 'severe')
6. TEAEs leading to death
7. TEAEs leading to study discontinuation
8. The TEAEs occurring under infusion and within 24 hours after the start of IMP infusion (Infusion related reaction (IRR))
9. Related TEAEs occurring within 24 hours after start of infusion
10. Adverse events of special interest (AESI):
 - Hypersensitivity/ Anaphylactic reactions/anaphylactic shock: Hypersensitivity (SMQ, restricted to narrow search), Anaphylactic reaction (SMQ, restricted to narrow search), "Anaphylactic shock conditions" (SMQ, restricted to narrow search)
 - Thrombogenicity: SMQ Embolic and thrombotic events (restricted to narrow search)
 - Transmission of infective agents: Preferred Term "Transmission of infectious agent via product" and "Suspected transmission of an infectious agent via product (Preferred Term)
 - Fibrinogen inhibitory antibodies: SOC"Investigations"
11. Related AESI:

- Hypersensitivity/ Anaphylactic reactions/anaphylactic shock: Hypersensitivity (SMQ, restricted to narrow search), Anaphylactic reaction (SMQ, restricted to narrow search), "Anaphylactic shock conditions" (SMQ, restricted to narrow search)
- Thrombogenicity: SMQ Embolic and thrombotic events (restricted to narrow search)
- Transmission of infective agents: Preferred Term "Transmission of infectious agent via product" and "Suspected transmission of an infectious agent via product (Preferred Term)
- Fibrinogen inhibitory antibodies: SOC"Investigations"

Additionally, number and frequencies of patients with TEAEs will be presented by decreasing frequency for all TEAEs, serious TEAEs and TEAEs considered related.

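### Part II adverse event tables give patient percentages and raw counts by age group but no rate per treated event or infusion, so the age columns may differ through exposure alone

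*SAP*

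**What the plan says.** Two unit statements stand side by side. Protocol 15.2.1 (Part II ODP/ODT) opens "With respect to the evaluation of efficacy, surrogate efficacy and safety of the single or repetitive intravenous infusions of BT524" and makes each bleeding event its own case in the primary analysis. SAP 4.1.2.2 repeats this ("evaluation of efficacy, surrogate efficacy and safety of the single or repetitive intravenous infusions of BT524, each bleeding event will be considered") and then, for adverse events, says that "the patient is the relevant unit for analyzing these endpoints". Protocol 15.2.6, the section specific to safety analysis, already uses the patient: "Incidence rates (i.e. number and percentage of affected patients) will be calculated for the coding levels" of system organ class and preferred term.

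SAP 11.1 carries out the patient-based rule. In the safety set, "number and frequencies (i.e. percentages) of patients with TEAEs will be given by System Organ Class" and preferred term, "together with the number of events for the following". For the overview of all adverse events, "the absolute count of AEs will be tabulated for each age group and overall". Counts therefore stand beside the percentages. No table in SAP 11.1 or the table list (Appendix 15.1) divides adverse events by treated events, infusions or patient-years.

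SAP 11.1 also sets the time at risk. In part II, treatment-emergent events are analysed only from treatment of a bleeding event to its Day 49 visit, or to an earlier point if another bleed intervenes. Related serious events are the exception and count at any time after first dose. Participation can be extended until the last directly enrolled part II patient finishes (Protocol 9 and 13.2).

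**The concern.** A patient treated for many bleeds has many risk windows, and a patient treated once has one. A percentage of patients with at least one event rises with the number of windows even if the risk per treatment is constant. Age groups are the columns of these tables, and possible follow-up differs between them by design. A reader comparing the under-6 column with the adult column could take a difference in exposure for a difference in safety, or miss a real difference that exposure offsets.

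The paediatric safety reading is what is at stake. The protocol's own precautions (11.7 and 13.5.2) link thrombosis risk to high or repeated dosing, and a patient percentage cannot express risk per administration.

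**Working it through.** The plan states no adverse event rate and no exposure total, so there is no figure to reproduce.

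**Step 1: possible follow-up (Protocol 13.2, planned dates).** First adult in 20 March 2013; first patient aged 6 to under 18 in 9 November 2014; first child under 6 planned for Q2/2018; last visit planned for Q1/2020. Days from first entry to 1 January or 31 March 2020, divided by 365.25:

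- adults: 6.78 to 7.03 years
- 6 to under 18: 5.14 to 5.39 years
- under 6 (entry 1 April to 30 June 2018): 1.51 to 2.00 years

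With the same end date for both groups, the adult-to-under-6 ratio lies between 7.03/2.00 = 3.5 and 6.78/1.51 = 4.5. These are ceilings for the first patient in each group, not observed exposure.

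**Step 2: effect of the number of treated events.** Let p be the risk of at least one treatment-emergent event per treated bleed and k the number of treated bleeds per patient. With equal risk in all groups and independence between bleeds, the expected share of patients affected is 1 − (1 − p)^k. Both p and k are assumptions, because the documents give neither.

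| p | k = 1 | k = 5 | k = 10 |
|---|---|---|---|
| 5% | 5.0% | 22.6% | 40.1% |
| 10% | 10.0% | 41.0% | 65.1% |
| 20% | 20.0% | 67.2% | 89.3% |

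**Step 3: the same case with an event denominator.** The synopsis plans about 36 patients in part II, with at least 6 in each of three paediatric bands, which leaves about 36 − 18 = 18 adults. Take p = 10%, 5 bleeds per adult and 1 per child under 6:

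- adults: 18 × 5 = 90 treated events, 9 of them with an adverse event, so 9/90 = 10% of events but 41.0% of patients
- under 6: 6 treated events, 0.6 expected with an adverse event, so 0.6/6 = 10% of events and 10.0% of patients

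The event-level figure is equal, as it should be under equal risk. The patient percentage differs fourfold.

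**Step 4: can a reader rebuild the rate from the planned tables?** Only roughly.

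- Numerator: adverse event counts come from the part II safety set. Age group is fixed at first treatment in that study part (SAP 5.2).
- Denominator: bleeding events by age group (SAP 6.2) and infusions per event (SAP 8.2) come from the event-based sets. The larger of these, FBE, requires at least one efficacy assessment (SAP 4.1.2.2), and age group is assigned afresh at each event (SAP 5.2).

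A treated event without an efficacy assessment leaves the denominator while its adverse events stay in the numerator. A child who passes 6, 12 or 18 years between events can contribute adverse events to one column and treated events to another.

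**The case against.** Much can be said for the plan, and three stronger readings that a reader might infer do not hold.

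First, that part II adverse events appear only as patient percentages. They do not: SAP 11.1 tabulates counts as well, and treated events and infusions per event are summarised by age group elsewhere. An approximate rate is available. This stands, subject to the mismatch in step 4.

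Second, that the SAP has abandoned the protocol's event-level unit for safety. Protocol 15.2.6 itself defines adverse event incidence by affected patients, and the SAP follows it. Event-level analysis is kept in part II for vital signs, inhibitory antibodies, laboratory data and physical examination (SAP 11.5, 11.6, 11.8, 11.10). What remains is a tension between a general and a specific sentence, which the protocol already contains. SAP 2.1 declares consistency with the protocol and does not explain it.

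Third, that adults will look less safe than young children. This needs more treated events per adult, and no event counts are given. Protocol 13.5.6 expects frequent trauma bleeds, dental care and circumcision in childhood, so young children could have more treated events per year. Calendar time acts mainly through the number of treated events, because other adverse events outside the windows are only counted and listed. A window also closes early when another bleed occurs, so time at risk does not grow by a full 49 days with each event.

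Finally, age results are descriptive (SAP 5.2), and the only confirmatory test concerns clot firmness (SAP 5.1). Nothing confirmatory is affected.

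**Conclusion.** The point holds in a limited form. The part II safety-set tables lack any rate per treated event or infusion, while time at risk accrues per treated event and possible follow-up differs about 3.5- to 4.5-fold between the first adults and children under 6. Patient percentages by age group may therefore differ through exposure alone. On the assumptions of step 2, going from 1 to 5 treated events moves the percentage from 5% to 23%, from 10% to 41% or from 20% to 67%. The size and direction in this trial cannot be derived from the documents. This is a worthwhile improvement to the safety tables, together with a clarification of the unit of analysis. It does not correct a departure from the protocol's adverse event section.

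**What to change.** In the part II safety-set tables of treatment-emergent events (overview, all, serious, related; Tables 14.3.1.2.4, 14.3.2.1.4, 14.3.2.2.4 and 14.3.2.3.4), add by age group and overall:

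- the number of treated events and of infusions, counting every treated event and not only those in FBE
- the crude number of treatment-emergent events per treated event and per infusion

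Use one age-assignment rule for numerator and denominator, and state it. Keep the patient percentages. Show related serious events with onset outside the 49-day windows separately, since they accrue over all follow-up. An interval that allows for several events per patient is optional and only for the overall total. With about six patients planned in each paediatric band, a model such as GEE by age group would be unreliable.

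Add a sentence to SAP 4.1.2.2 reconciling its two unit statements, and note in SAP 2.1 how Protocol 15.2.1 and 15.2.6 are read together.

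The cost is a few columns from data already collected, and slightly longer tables.

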5.1 General statistical methods

All data collected will be analyzed using appropriate statistical methods for the production of all tables, listings and figures and for the statistical analysis.

Data will be summarized with respect to demographic and baseline characteristics, efficacy and safety observations and measurements (cf. section 4). Tabulations will be presented for each parameter. Generally, age subgroups will be presented in columns and overall totals will be provided, too. Data will be presented for the overall population, and for ODP and ODT, each for minor events, major events and overall in rows, as specified in the section for the respective parameter.

For continuous variables descriptive statistics will be given including mean, SD, median, quartiles, minimum, and maximum. Additionally, for PK data, efficacy and safety parameters 95 % confidence intervals will be calculated where appropriate. Categorical data will be presented in frequency tables using counts and percentages. In addition, the number of patients with missing values will be displayed. Percentages relate to the number of patients (or events, for part II) with data. This includes data obtained by the respective missing data replacement strategy (see section 5.3 Missing data).

Means and medians will be presented by 1 additional decimal place and standard deviation will be presented by 2 additional decimal places than the standard presentation level of the respective patient data. Minimum and maximum values will be presented using the same number of decimal places as the patient data. Percentages will be presented to 1 decimal place if not otherwise stated. Statistical tests will be performed descriptively, two-sided if not specified otherwise. Only the one test of a secondary efficacy endpoint of part I (1-hour post-end to pre-value of MCF) is considered confirmatory. A (two-sided) p-value less than 0.05 will then be considered statistically significant. The confidence level for calculation of confidence intervals will be chosen as (1-significance level) of the respective statistical test. All collected data will also be presented in listings (cf. separate tables shells document). Only additional special listings such as for protocol deviations (cf. section 6.3), bleeding history (cf. section 7.3), AEs leading to death (cf. section 11.2), AEs leading to discontinuation (cf. section 11.3), or normal ranges (cf. section 11.8) are explicitly referred to within the applicable section. In listings, data will be sorted by site, and patient, and when appropriate by visit or other identifiers for sequence or type of observation.

5.2 Subgroups

For analyses, patients are assigned to the following age subgroups: Adults (18 to 75 years), adolescents (12 to < 18 years), children (6 to < 12 years), and children < 6 years. The group < 6 years will in addition be subdivided into pre-school children (2 to < 6 years), infants and toddlers (28 days to < 2 years), and newborns (0 days to 27 days).

For patient-based analyses using the APE set, patients will be assigned to age subgroups according to their age (years) as derived from date of birth (year) as age at date of ICF signature for each of the study parts.

For patient-based analyses using the SAF, FAS, PP, or PK set in both study parts, patients will be assigned to age subgroups according to the age group assessment provided for their first BT524 treatment in the respective study part.

For the event-based analysis (FBE, PPBE) in part II, each bleeding event will be assigned to the age subgroup according to the age group assessment provided for the specific bleeding event.

Another subgroup for event based analysis is ODP/ODT with major/minor classification.

Results for the different subgroups will be presented descriptively by presenting the results for selected analyses (as defined in the respective section) separately for each subgroup and the overall population.

5.3 Missing data

5.3.1 Missing severity assessment for adverse events

If severity is missing for an AE starting prior to the administration of IMP, then a severity of “Mild” will be assigned. If the severity is missing for an AE starting on or after administration of IMP, then a severity of “Severe” will be assigned. The imputed values for severity assessment will be used for incidence summaries, while the actual values will be used in data listings.

5.3.2 Missing relationship to investigational product for adverse events

If the relationship to investigational product is missing for an AE starting on or after the administration of IMP, a causality of “Related” will be assigned. The imputed values for relationship to investigational product will be used for incidence summaries, while the actual values will be presented in data listings.

5.3.3 Missing seriousness assessment for adverse events

If no information about seriousness is available, the AE will be considered serious. The imputed values for seriousness assessment will be used for incidence summaries, while the actual values will be used in data listings.

5.4 Handling of partial dates and missing/incomplete times

For prior or concomitant medications, incomplete (i.e., partially missing) start date and/or stop date will be imputed. When the start date and the stop date are both incomplete for a patient, impute the start date first.

For AEs, incomplete (i.e., partially missing) start dates and times and/or incomplete stop dates and times will be imputed.

Imputation rules for incomplete dates for prior or concomitant medications, incomplete dates and times for AEs are described in sections 5.4.1 and 5.4.2.

5.4.1 Incomplete start date and time

The following rules will be applied to impute the missing numerical fields. If the stop date is complete and the imputed start date is after the stop date, then the start date will be imputed using the stop date.

Missing day and month

- If the year of the incomplete start date is the same as the year of the date of the first dose of investigational product, then the day and month of the date of the first dose of investigational product will be assigned to the missing fields.

- If the year of the incomplete start date is before the year of the date of the first dose of investigational product, then December 31 will be assigned to the missing fields.
- If the year of the incomplete start date is after the year of the date of the first dose of investigational product, then 01 January will be assigned to the missing fields.

Missing month only

- The day will be treated as missing and both month and day will be replaced according to the above procedure.

Missing day only

- If the month and year of the incomplete start date are the same as the month and year of the date of the first dose of investigational product, then the day of the date of the first dose of investigational product will be assigned to the missing day.
- If either the year is before the year of the date of the first dose of investigational product or if both years are the same but the month is before the month of the date of the first dose of investigational product, then the last day of the month will be assigned to the missing day.
- If either the year is after the year of the date of the first dose of investigational product or if both years are the same but the month is after the month of the date of the first dose of investigational product, then the first day of the month will be assigned to the missing day.

Missing/Incomplete Time

- If the time is missing and the date is complete and is the same as the date of the first dose of investigational product, or the date is imputed to be this date, then the time will be set to the time of the first dose of investigational product. Otherwise, missing times will be imputed as 00:00.
- If the minutes are given but the hour is not, then the time will be regarded as completely missing and handled as above. If the hour is given but the minutes are not, then if the hour is the same as the hour of the first dose of investigational product, then the minutes of that dose of investigational product will be assigned to the missing fields. Otherwise 00 will be assigned to the missing minutes.

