5.5 Observation and analysis times

Study periods or stages

The study primarily differentiates between the two parts, part I (PK/PD) and part II (ODP/ODT). Within each part different periods are defined:

Part I:

- Screening period: Day -17 to Day -1
- PK/PD assessment/sampling period:
 - Hospitalization from Day 0 (IV infusion) through Day 2
 - Subsequent PK FU from Day 4 through Day 14
- PK safety FU period ending with the PK safety visit at Day 49 (+/- 4)

Accordingly, the participation time for part I is defined as time from screening visit (ICF date) until PK safety visit and defines the analysis time for part I.

Part II periods differ depending on conduct (with or without hospitalization) but are usually ending with the follow up safety visit at Day 49 (+/- 4). Please see the protocol (e.g. section 3) for more details.

Accordingly, the participation time of patients for part II starts

- ⇒ at screening visit (ICF date) for patients solely enrolled in part II or
- ⇒ at 1st day after part I PK safety visit for patients enrolled into part I/II

and lasts until the date of patients study completion/termination.

For the patient based analysis in part II the analysis time is defined by the participation start time until the safety visit (Day 49 +/- 4) of the patients last treated bleeding event.

For the bleeding event based analysis in part II the analysis time of a bleeding event starts with its Treatment Day 0 and ends with its safety visit. Accordingly, data from in-between

individual 49 day periods or after last Day 49 visit will only be listed and not included in the analysis.

For adverse events reporting related periods are defined:

- Patient Enrolment to the First Administration of Study Drug (NTEAE)
- After first Administration of Study Drug until respective Day 49 visit (part I and part II) (TEAE)
- In-between individual 49 day periods or after last Day 49 visit (only related SAEs will be listed and included in the analysis), all other AEs will be counted and listed.

For concomitant medication please refer to section 9.

Study days and bleeding event number

Primarily, study days are counted since first dose of study medication (i.e. in part I) up until the end of study participation.

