Because the study is divided into parts with the possibility of multiple bleeding events in part II, study days are additionally considered for each part II bleeding event separately. More precisely, study day is also defined as the number of days since first dose of study medication of the applicable part II bleeding event and, for a particular date, is calculated as:

$$\text{Study day} = \text{Assessment date} - \text{Date of first dose of study medication for this bleeding event}$$

Due to consideration of several bleeding events as individual cases and the repeated observation periods in part II, related events will be numbered per patient, sorted by start date and time of the events associated with part II participation.

Definition of baseline values

Part I: The baseline value is defined to be the last value, which was assessed during screening before and up to PK dosing Day 0 (all pre-dose). In other words, if for example pre-dose value of fibrinogen antigen at Day 0 of PK is missing, baseline will use the value measured at the screening visit.

Part II: For event-based analysis in part II, baseline value is defined to be Day 0 (pre-dose) per event. In case this is not available, for fibrinogen antigen and fibrinogen activity the baseline values from last event will be used. For all other values Day 0 (pre-dose) will not be replaced, if missing.

Definition of analysis time points or time windows

The following definition of analysis time points, time windows and measurement assignments applies unless specified differently in the respective sections. In particular, for PK parameter specific decisions, the definitions in the PK analyses plans prevail.

Time points for the different endpoints to be measured are specified in the protocol, e.g. in the flowcharts. For each endpoint measurements are taken at an (individual) selection from

time points during Screening, on Day 0 (pre- as well as post-dose) and/or on Days 1, 2, 4, 7, 10, 14 or 49.

Time windows for measuring times are not provided except for the Day 49 measurements, where the window is +/- 4 days. Therefore, no exclusions due to window deviations will be applied. For the PK analysis, actual times will be used. Should time windows be set-up (at a later stage) and result in exclusions of data from analyses, this will be documented in an amendment to this SAP or - at the latest - by means of the applicable data review meeting minutes prior to data base lock.

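### SAP 5.4.1 dates incomplete AE onsets from the first dose only, so the infusion-reaction tables can lose events at later infusions and gain false ones at the first dose

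*SAP*

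**What the plan says.** SAP 5.4 applies its imputation rules to AE start dates and times. In 5.4.1 the only dosing reference is the first dose of investigational product:

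- **Time missing.** If the AE date is, or is imputed to be, the first-dose date, the first-dose time is used. "Otherwise, missing times will be imputed as 00:00".
- **Minutes missing.** If the hour equals the first dose's hour, that dose's minutes are used. "Otherwise 00 will be assigned to the missing minutes".
- **Day missing.** In the first-dose month, the first-dose day is used. In a later month, "then the first day of the month will be assigned to the missing day".
- **Day and month missing.** In the first-dose year, the first-dose date is used.
- **Guard.** The one consistency check is conditional: "If the stop date is complete and the imputed start date is after the stop date", the stop date is used. Nothing corrects a start that is too early.

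The safety tables use other clocks. SAP 11.1 (items 8 and 9; Tables 14.3.2.9.x and 14.3.2.10.x) counts TEAEs during infusion and within 24 hours of its start. For TEAEs generally, 11.1 says "for part II this is for each bleeding event the duration between treatment of the bleeding event and Day 49 safety visit"; a further bleed closes the window sooner. TEAEs outside these frames are only counted and listed, apart from related SAEs. For the event-based analysis, SAP 5.5 says "the analysis time of a bleeding event starts with its Treatment Day 0 and ends with its safety visit".

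**The concern.** A first-dose anchor suits a trial with one start of treatment. Here BT524 is given again, singly or repeatedly, over at least 12 months, and the safety clock restarts each time. A rule tied to one dose cannot place a partial onset correctly around any other.

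The IRR tables are where repeat exposure to a plasma protein would show a signal, and the groups are small. SAP 5.3 imputes towards caution: missing severity after dosing becomes severe, missing relationship becomes related, and missing seriousness becomes serious. At a later infusion, 5.4.1 moves a same-day AE away from the drug with no reason given. At the first dose it does the opposite and pulls AEs of unknown day onto the infusion.

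**Working it through.** There is no stated figure to reproduce, so the check applies the rules as written.

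**Which dose is the anchor?** In defining study days, SAP 5.5 glosses first dose as the Part I dose. When it means the per-event dose it says so: "study day is also defined as the number of days since first dose of study medication of the applicable part II bleeding event". SAP 5.4.1 has no such qualifier. The first dose is therefore the Part I dose for Part I patients, and the first Part II infusion for patients enrolled directly into Part II.

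**Worked example (dates assumed).** First dose 05-Mar-2018 09:00; one later Part II infusion 17-Oct-2018 10:30.

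| AE as recorded | Imputed onset | IRR tables | TEAE window (if applied to imputed onset) |
|---|---|---|---|
| 17-Oct-2018, no time | 17-Oct 00:00, 10.5 h before infusion | out | out by date and time; in by date |
| 17-Oct-2018, hour 10, no minutes | 10:00, 30 min before | out | out by date and time; in by date |
| 18-Oct-2018, no time | 18-Oct 00:00, 13.5 h after | in | in |
| Oct-2018, no day | 01-Oct 00:00, 16 days before | out | gap: counted and listed only |
| 2018, no day or month | 05-Mar 09:00 | in, at the first dose | Part I |
| Mar-2018, no day | 05-Mar 09:00 | in, at the first dose | Part I |

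The first two rows stay in the IRR tables only if another infusion in the previous 24 hours covers the imputed time. The second also stays in if the infusion began on the hour. The last two rows enter by imputation alone.

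**Conditional size.** These shares apply only given a partial onset. They assume infusion starts uniform over 08:00–16:00 and uniform onsets; neither is in the documents.

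- *Missing time, later infusion, true onset within 24 h, no infusion in the previous 24 h.* The AE is lost if onset falls on the infusion date, with probability (24 − start hour)/24: 16/24 = 67% at 08:00, 12/24 = 50% at 12:00, 8/24 = 33% at 16:00; average 50%. If onset is within 12 h: (4 × 1 + 4 × 10/12)/8 = 92%.
- *Missing minutes, later infusion.* With start minutes m spread evenly over 0–59, the share lost for onset within 1 h is Σ(60 − m)/60², m = 1 to 59, which is 1,770/3,600 = 49%. Within 2, 4 and 24 h this is divided by 2, 4 and 24: 25%, 12%, 2%. With on-the-hour starts it is 0%.
- *Missing day, later infusion, onset uniform over 49 days.* With mean month length 365.25/12 = 30.44 days, about 15.2 days of the infusion month remain on average: 15.2/49 = 31% fall in that month. Infusions on the 1st (about 2 points) are not misdated, so 29% are dated before the infusion. If the previous treatment was the Part I dose, all of these leave the Part II tables. If it was a Part II event, only those landing in a gap do: 0% when it was 49 days earlier and its safety visit fell on day 49, about 16% at 60 days, 29% at 80 days or more.
- *Missing day in the infusion's month, true onset within 24 h.* About (1/49)/0.31, roughly 6.5%. If all onsets fall within 7 days it is 16%. So anchoring such AEs on the infusion, as 5.4.1 does at the first dose, is mostly wrong under either assumption.

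**Scale of one event.** With about 36 patients (Protocol 11.1.5), 1/36 = 2.8% (95% CI 0.1–14.5%) against 0/36 (0–9.7%). With 6 children under 6 years (Protocol synopsis), 1/6 against 0/6.

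**The case against.** **First dose may mean first dose of the event.** The contrast in SAP 5.5 points the other way. Even on that reading, repeat infusions within one event, which SAP 8.2 tabulates, would have no anchor.

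**The TEAE loss is not certain.** SAP 11.1 speaks of TEAEs *reported* within the frames, while its related-SAE exception speaks of onset. If the report date governs, a missing-day AE does not leave the tables. If windows run by date from Treatment Day 0, an untimed same-day AE does not leave either. This stands, so the TEAE part depends on the reading.

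**Moving an AE between events does no harm.** A reader might infer that dating an AE into an earlier Part II event distorts the tables. It does not: SAP 4.1.2.2 makes the patient the unit for AEs, and the AE tables are patient-based. Only a move to Part I or into a gap matters.

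**Partial onsets should be rare.** Protocol 14.5.1.1 has patients asked about AEs during infusion and at visits. Part II adds calls on Days 1, 2, 5 and 10, or in-hospital assessment, and Protocol 16.1 requires queries until resolved. Related SAEs stay in the analysis whatever their onset, and Listing 16.9.1 shows every AE. All this limits the size but does not make the rule right.

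**Conclusion.** The defect is real and minor. The IRR misclassification at later infusions follows from the text on every reading considered, and so does the spurious entry at the first dose. The Part II TEAE loss is conditional on windows being applied to imputed onset.

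A reader might infer that the IRR tables as a whole understate reactions, or that first doses are handled correctly and only later ones are wrong. The documents support neither. In the Part I tables, with one infusion per patient, the error is an overcount. In the Part II tables it is an undercount at later infusions and an overcount at the first infusion of patients enrolled directly. Tables 14.3.2.9.1 and 14.3.2.10.1 pool both parts, so their net direction is unknown.

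The number of AEs affected cannot be derived. The percentages describe what happens to a partial onset once it exists and do not show that any reported table would change. Protocol 14.6.2 helps with the gap cases: between 49-day periods only related serious TEAEs are recorded, so any other AE imputed into a gap is probably an artefact.

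**What to change.** 1. In SAP 5.4.1: if the AE date is the date of any BT524 infusion and the time is missing, or the hour matches that infusion's hour and the minutes are missing, and no record shows a pre-dose onset, set onset to the start of that infusion (the first that fits). Otherwise keep the present default.
2. In SAP 11.1: state that the TEAE window runs by onset date from Treatment Day 0 of each event.
3. For a missing day, or missing day and month: if the known date parts overlap a treatment-to-Day-49 window and nothing recorded contradicts it, keep the AE in the TEAE tables. If several windows or both parts fit, use the visit or event under which it was reported. Do not put it in the IRR tables on imputation alone, at the first dose or later; show it separately as a possible IRR with day unknown.
4. Flag imputed onsets in Listing 16.9.1.

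The cost is SAP wording and a small change to the AE derivation; no new data are needed. The drawback is that a few untimed Day 0 complaints that really began before dosing will count as IRRs. For a background complaint spread evenly over the day, 8/24 = 33% (08:00 start) to 16/24 = 67% (16:00 start) would be pre-dose. Protocol 13.1.2.2 and 13.1.2.4 assess AEs separately before and after infusion on Day 0, so many of these can be identified, and the flag shows the rest.
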